Ultrasound guidance to facilitate placement of peripheral nerve blocks has been shown to improve the onset time of analgesia, increase success of the block, reduce vascular puncture and increase patient satisfaction.²⁻³ While various ultrasound-guided techniques for single-shot saphenous block have been described in the literature, currently no description of an ultrasound-guided continuous saphenous nerve block is available.⁴⁻⁹ This study will employ an ultrasound-guided technique for continuous saphenous block and describe this technique.

Continuous femoral nerve block is a common practice and could also be used with sciatic block to provide analgesia of the medial ankle instead of a saphenous block. Continuous saphenous block, however, has potential advantages over an inguinal femoral nerve catheter including less bacterial colonization, and preservation of quadriceps motor function.¹⁰ This study will assess the effect of continuous saphenous block on quadriceps function.

Objectives

This study will evaluate the effect of adding a continuous saphenous nerve catheter to a continuous sciatic nerve catheter in patients undergoing ankle surgeries. Specifically, patients undergoing ankle fusions or open reduction and internal fixation of bi- or tri-malleolar fractures will be evaluated. The primary endpoint of this study will be the verbal pain score at rest and with movement at 48h post-nerve blockade. At this point in time the primary saphenous nerve

block will have resolved, and any saphenous analgesia will be due to the infused solution. Secondary endpoints of opioid use, nausea and vomiting, sleep disturbance, and change in quadriceps strength will also be evaluated. Additionally, we will describe an ultrasound guided technique for placement of a continuous saphenous nerve catheter supported by cadaveric dissection.

Methods and Measures

Design

The study will be a randomized, double-blind, placebo-controlled trial. Patients will be recruited and have sciatic and saphenous perineural catheters placed as described below, and initial nerve blocks produced in the usual fashion. Patients will then be randomized to either an active drug (local anesthetic) or a placebo (saline) infusion group at the time of saphenous infusion preparation by Pharmacy personnel.

Setting

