Study participants will be asked to report a preoperative baseline pain score (Numeric Pain Scale (0-10)), and have quadriceps strength measured (see below) prior to any sedation being administered. Patients will undergo placement of a continuous subgluteal sciatic nerve catheter, and dosage with 25ml of 0.25% bupivacaine with epinephrine 1:200,000 and clonidine 25 mcg per usual technique after sedation. A perineural catheter will then be placed for primary saphenous nerve block and postoperative saphenous infusion. This continuous saphenous catheter will be placed using ultrasound guidance (Sonosite Turbo™, Bothell, WA) (6-13MHz linear probe). The superficial femoral artery will be identified in short axis at approximately the midpoint or distal third of the femur as the artery lies deep to the sartorius muscle in the adductor canal. Using aseptic technique, an 18 gauge tuohy needle will be inserted in-plane from lateral to the transducer and advanced to a position anteromedial to the artery, between sartorius and vastus medialis muscles. Proper positioning will be confirmed by injection of saline, a 20g multiorifice catheter will be inserted 3-4 cm beyond the needle tip and the catheter will be tunneled and taped up the medial surface of the thigh. The catheter will be test dosed with 1.5% lidocaine with 1:200,000 epinephrine to confirm position and rule out IV injection. The primary saphenous nerve block will be produced by incremental injection through the catheter of 10ml of 0.25% bupivacaine with epinephrine 1:200,000 and clonidine 15 mcg. Successful saphenous block will be defined as loss of sensation to pinprick in the mid, anteromedial leg measured at 15 and 30 minutes post-block. A 3-point scale will be used to define sensory block: 0=full sensation, 1= touch without sharp sensation, 2=absent sensation.

To determine the effect of saphenous block on quadriceps function, patients will have knee extension muscle strength tested pre-block and 30 min post-block using a Hoggan Health microFET 2 MT Digital Handheld Dynamometer. After placement of both the saphenous and sciatic nerve catheters, patients will receive either neuraxial or general anesthesia for surgical anesthesia at the discretion of the attending anesthesiologist medically directing their primary anesthetic technique.

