Patients with evidence of sciatic and saphenous nerve block will be randomized to receive a postoperative continuous infusion of either saline (control) or 0.2% ropivacaine by elastomeric infusion pump at 5ml/h started within 6h of catheter placement. The randomization will occur by sealed envelope provided to the OR Pharmacy (block randomization in blocks of 10) and the OR pharmacy will prepare the 300 ml elastomeric pump with active or control solution. The On-Q C-Bloc™(300ml capacity) (I-Flow corporation) pump will be attached to the saphenous catheter in the PACU, or within 6h of primary block; the catheter will infuse for 60 hours.

The patients, physicians, nurses and investigators will be blinded to treatment group.

The sciatic infusion will be managed per usual practice: postoperatively all patients will receive 0.2% ropivacaine through their sciatic nerve catheter at a basal infusion rate of 10ml/h, . The sciatic pump will be an On-Q™ pump per usual practice. All patients will have oral and IV opioids prescribed while hospitalized, and oral opioids prescribed after hospital discharge. In the event of breakthrough pain, patients will be instructed to adjust the sciatic nerve pump, and/or to take oral opioids for the pain.

While patients are hospitalized, opioid administration and pain scores will be recorded by nursing staff on the patient care record. Side effects including nausea, vomiting, or itching will also be recorded. Patients will be seen on a daily basis while in the hospital by the acute pain service, and adjustment of their sciatic infusion performed if indicated. They will be questioned about sleep quality, pain score, opioid side effects, and sensory function in the sciatic and saphenous distributions. This information will be recorded by the acute pain management team. On postoperative day 1, all patients will again have their quadriceps muscle group strength assessed with the hand-held dynamometer, and the catheter sites will be inspected per standard protocol.

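### The 30-minute quadriceps change is uncontrolled and precedes randomisation; the postoperative day 1 comparison between arms should be fixed in advance as ANCOVA on pre-block strength

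*Combined protocol and SAP*

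**What the plan says.** The Background states the aim: "This study will assess the effect of continuous saphenous block on quadriceps function". Quadriceps strength is a secondary endpoint, described as a change in strength under Objectives and as a reduction under Outcome Measure(s).

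Strength is measured three times, all described under Interventions and Interactions:

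- **Baseline.** Patients will "have quadriceps strength measured (see below) prior to any sedation being administered".
- **30 minutes after the block.** The purpose is given as: "To determine the effect of saphenous block on quadriceps function, patients will have knee extension muscle strength tested pre-block and 30 min post-block".
- **POD1.** "On postoperative day 1, all patients will again have their quadriceps muscle group strength assessed with the hand-held dynamometer".

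On allocation, the Design section, after describing catheter placement and the initial blocks, says: "Patients will then be randomized to either an active drug (local anesthetic) or a placebo (saline) infusion group". Interventions and Interactions adds a condition: "Patients with evidence of sciatic and saphenous nerve block will be randomized to receive a postoperative continuous infusion". The saphenous pump is attached in the PACU or within 6 h of the primary block. On masking: "The patients, physicians, nurses and investigators will be blinded to treatment group".

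The Analytical Plan prefers the general linear model, with the t-test as its example. For secondary endpoints it lists t-tests, Mann-Whitney U and chi-square tests at p < 0.05. It gives no time point, baseline or model for quadriceps strength.

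**The concern.** There are two linked problems.

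First, the 30-minute change is given a causal purpose that it cannot serve. It is a single-group before-and-after difference that spans several steps, and it is complete before the randomised infusion starts. A loss of strength could come from sedation, the sciatic block, the saphenous block or a mixture, and no comparator separates them.

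Second, the measurement that can answer the stated aim, POD1 strength by arm, has no specified analysis. Two post-baseline times and three ways of handling baseline all fit the wording. At stake are the precision of the only randomised evidence on quadriceps function, and protection against choosing between versions once the data are seen.

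**Working it through.** **1. Order of events (Design; Interventions and Interactions)**

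| Step | Who receives it | Relation to randomisation |
|---|---|---|
| Baseline strength, before sedation | all | before |
| Sedation, then sciatic catheter and dose | all | before |
| Saphenous catheter, lidocaine test dose, primary saphenous dose | all | before |
| Strength at 30 min | all | before |
| Randomisation of patients with evidence of both blocks; ropivacaine or saline infusion starts | by arm | at |
| Strength on POD1 | by arm, blinded | after |

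The baseline-to-30-minute change spans rows 1 to 4, with no control at any point. The documents give no figure from which the share due to sedation or the sciatic dose could be sized. Only the last row is a randomised comparison.

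**2. The plan's own sample size**

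Inputs (Sample Size): d = 0.74, two-sided alpha 0.025, power 0.80. The two-sample t-test (noncentral t) gives n = 36.002, rounded up to 37 per arm and 74 in total; power at 37 is 0.812. The stated figure reproduces, and 37 per arm is used below.

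**3. Precision of the POD1 contrast**

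Let r be the correlation between pre-block and POD1 strength. The documents give neither r nor an SD for strength, so r = 0.3 to 0.9 is an assumed range and results are in SDs of POD1 strength. Variance relative to raw POD1 strength:

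- change score: 2(1 − r), assuming equal SDs at both times
- ANCOVA: 1 − r²

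The 95% CI half-width is t(0.975, df) × √(2 × factor/37), with df = 72 for raw and change and 71 for ANCOVA. For raw strength this is 1.993 × √(2/37) = 1.993 × 0.2325 = 0.463. For ANCOVA at r = 0.5 it is 1.994 × √(2 × 0.75/37) = 0.401.

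| r | Factor, change | Factor, ANCOVA | Half-width, raw | Half-width, change | Half-width, ANCOVA |
|---|---|---|---|---|---|
| 0.3 | 1.40 | 0.91 | 0.463 | 0.548 | 0.442 |
| 0.5 | 1.00 | 0.75 | 0.463 | 0.463 | 0.401 |
| 0.7 | 0.60 | 0.51 | 0.463 | 0.359 | 0.331 |
| 0.9 | 0.20 | 0.19 | 0.463 | 0.207 | 0.202 |

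Allowing for chance baseline imbalance multiplies the ANCOVA variance by 1 + 1/70, giving half-widths of 0.445, 0.404, 0.333 and 0.204. With that allowance ANCOVA beats raw strength once r² > 1/71, that is, r above about 0.12.

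**4. Detectable difference (80% power, two-sided 0.05, noncentral t) and equivalent sample size, 37/(1 − r²)**

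| r | Raw | Change | ANCOVA | Raw n per arm matching ANCOVA |
|---|---|---|---|---|
| 0.3 | 0.660 | 0.781 | 0.630 | 40.7 |
| 0.5 | 0.660 | 0.660 | 0.572 | 49.3 |
| 0.7 | 0.660 | 0.511 | 0.472 | 72.5 |
| 0.9 | 0.660 | 0.295 | 0.288 | 194.7 |

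**5. Cost of leaving the choice open**

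I simulated 60,000 trials per r with 37 per arm, bivariate normal strength and no treatment effect. The chance that raw or change gives p < 0.05 was 0.087, 0.090, 0.095 and 0.095 at r = 0.3, 0.5, 0.7 and 0.9. Each test alone stayed at about 0.05.

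**The case against.** The strongest reply is that no wrong analysis is actually planned. The sentence about the 30-minute test speaks of saphenous block, not continuous block, and nothing says that change will be compared between arms. The aim for the continuous block is served by the POD1 test, and the general linear model wording already allows ANCOVA. All of this is true: the second problem is one of under-specification.

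Other points that stand in whole or part:

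- **The 30-minute change is not worthless.** A paired mean change with a confidence interval is a legitimate description. If sedation and the sciatic block act at all, one would expect them to lower strength, so little or no loss would still be informative. What fails is attributing a loss to the saphenous block.
- **The lidocaine test dose** ("The catheter will be test dosed with 1.5% lidocaine") goes through the saphenous catheter, so it is fairly counted as part of that block. Sedation and the sciatic dose remain.
- **Raw and change-score t-tests are both unbiased under randomisation.** The case for ANCOVA is precision and a fixed choice, not removal of bias.
- **The gain depends on r.** At r = 0.3 it is small (0.46 to 0.44 SD), and nothing in the documents supports r = 0.9.
- **The change-score figures assume equal SDs.** If k is the POD1 SD divided by the baseline SD, change scores are less precise than raw when r < 1/(2k): below 0.33 at k = 1.5 and below 0.71 at k = 0.7. ANCOVA's factor 1 − r² does not depend on k. In baseline-SD units the change-score variance exceeds ANCOVA's by (1 − rk)², which is never negative, so ANCOVA's lead survives.
- **The 9% is a worst case.** The plan does not propose reporting the smaller p-value.

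**Conclusion.** The concern holds, as a minor point on a secondary endpoint. The order of events is clear from the text: the 30-minute change is uncontrolled, precedes randomisation and the infusion, and cannot establish the effect of the saphenous block. POD1 strength by arm is the only randomised, blinded quadriceps measure, and its analysis is not fixed.

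In this range of r, ANCOVA on pre-block strength narrows the 95% CI half-width for POD1 by between about 5% (0.442/0.463 = 0.95) and 56% (0.202/0.463 = 0.44) relative to raw strength, and is the most precise of the three options throughout. These sizes rest on assumed correlations and 37 evaluable patients per arm; the change-score figures also assume equal SDs. The contribution of sedation and the sciatic block to the 30-minute change cannot be sized. The primary analysis and sample size are not affected.

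**What to change.** 1. **Analytical Plan.** Name the quadriceps analysis: POD1 strength compared between arms by ANCOVA with pre-block strength (not the 30-minute value) as covariate, reported with a 95% CI. State that it estimates ropivacaine versus saline infusion after a primary block in all patients. Note that the contrast may be diluted if that block persists on POD1; the Background gives 12-24 h of analgesia for the usual single-shot block.
2. **Interventions and Interactions.** Relabel the pre-block to 30-minute change as descriptive of sedation, sciatic block and saphenous block together.
3. **Data collection form** (listed in the Appendix, not shown). Record hours since block at the POD1 test, if the form does not already do so.

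The cost is wording in two sections and at most one extra data field. Pre-block and POD1 strength are already collected, so no test, visit or patient is added.

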NCT01167907

WFUHS 00013823

PROTOCOL

Evaluation of Continuous Saphenous Nerve Block to Supplement a Continuous
Sciatic Nerve Block After Ankle Surgery

September 30, 2010

Study Title: Evaluation of a Continuous Saphenous Nerve Block to Supplement a Continuous Sciatic Nerve Block for Postoperative Analgesia Following Ankle Surgery

Principal Investigator: [name] MD

Co-investigator(s): [name] MD

Sponsor or funding source: Department of Anesthesiology at Wake Forest University Baptist Hospital. Pumps for saphenous infusion provided by I-Flow Corporation

Background, Rationale and Context

Orthopedic surgery of the lower extremity is particularly painful, and epidural analgesia or long-acting nerve blocks are commonly employed to reduce post-operative pain. Unilateral peripheral nerve blocks have advantages over epidural analgesia including: limited sympathetic blockade, no interference with bladder or contralateral limb function, and the ability to be discharged to home with a perineural catheter and pump for local anesthetic administration.¹ Patients undergoing ankle arthrodesis or bi/tri-malleolar fracture repairs are expected to have pain primarily in the sciatic nerve distribution, with a lesser component of their pain emanating from the medial side of the lower extremity innervated by the smaller, cutaneous saphenous nerve. At our institution, pain from this surgery is typically managed with a continuous sciatic nerve block maintained for 48-72h, and a single-shot saphenous or femoral nerve block with long-acting local anesthetic to provide 12-24h of saphenous analgesia. In spite of this aggressive regional analgesia approach, many patients still complain of significant pain in the postoperative period, and this study is designed to assess the analgesic effect of a continuous rather than single-shot saphenous block. We hypothesize that patients will have a clinically important reduction of pain score from a longer duration of saphenous nerve block provided by a continuous catheter, which would justify the added complexity of 2 perineural catheters

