All patients in the study will be undergoing non-urgent surgery at Wake Forest University Baptist Medical Center. The interventions will be performed in the regional anesthesia area of the surgery center. Patients will remain in the hospital at least one night, and once discharged, all patients will have daily follow-up by phone with the regional anesthesia acute pain management team.

Subject selection criteria

Patients undergoing non-urgent unilateral ankle arthrodesis or open reduction and internal fixation of bi/tri malleolar fractures will be recruited for the study.

- Inclusion Criteria**

Patients will be eligible for inclusion in the study if they are between the ages of 18-75 and are scheduled to undergo unilateral ankle arthrodesis or open reduction and internal fixation of bi/tri malleolar fractures at Wake Forest University Baptist Medical Center. Patient must give written informed consent for anesthesia including continuous sciatic nerve block and saphenous block for postoperative analgesia prior to recruitment. Patients must be able to comprehend the use and care of the catheters and infusion pump systems both in the hospital, and at once discharged home with verbal and written instructions

- Exclusion Criteria**

Patients will be excluded if they have a contraindication to saphenous or sciatic nerve blockade (including significant coagulation abnormalities), history of opioid addiction, current chronic pain therapy with high-dose opioid (extended release opioids or > 40mg oxycodone equivalents per day), allergy to study medications, or failure to place a sciatic catheter. Failure to achieve successful sciatic analgesia or a successful primary saphenous block will also lead to exclusion.

- Sample Size**

74 patients will be recruited for the study and will be randomized into two groups of $n = 37$ patients each. This sample size provides power = 0.80 to allow reliable detection of group differences of $d = 0.74$ standard deviation units (approximately 1.5 points on a 0 -10 pain scale in our pilot data), assuming two-sided inferences held to the $\alpha =$

0.025 level (see stats section for details on error control). Differences smaller than this magnitude are unlikely to be clinically meaningful.

Interventions and Interactions

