Patients will be generally discharged home with peripheral nerve catheters in place on POD #1, after receiving written and verbal instructions in perineural catheter management. These patients will be called at 24 and 48 hours post discharge to determine rest and incident numeric pain scores, opioid usage, sleep quality (as number of awakenings for pain), and the presence of nausea or vomiting. Patients will be given contact numbers and instructions to call with any questions or concerns per usual practice.

Outcome Measure(s)

The primary endpoint of this study will be a reduction of the rest and incident verbal pain scores 48hpost-nerve blockade when the primary saphenous single-shot block is expected to have resolved. Secondary endpoints of reduction of opioid use, nausea and vomiting, sleep disturbance (as number of awakenings), and reduction of quadriceps strength will also be evaluated. Additionally, we will describe an ultrasound guided technique for placement of a continuous saphenous nerve catheter supported by cadaveric dissection.

Analytical Plan

All analyses will be conducted with SAS 9.2 (SAS, Inc., Cary, NC). Prior to conducting the primary analysis, the distributional characteristics of all variables will be considered by examining histograms and descriptive statistics. Where possible, all analyses will be conducted using the general linear model (e.g., t-test), but where necessary nonparametric equivalents will be conducted for pairwise comparisons (e.g., Mann-Whitney U). As a result of random assignment, participant characteristics are expected to be similar, but treatment group characteristics will be compared using descriptive statistics. The primary analysis will consist of a direct comparison between treatment groups at 48 hours using an independent t-test. Because the primary analysis consists of two comparisons (i.e., pain with rest and pain with movement), each comparison will be evaluated at the $\alpha = 0.025$ level (i.e., holding the family to a conservative 5% type-I error rate). Secondary analyses will be conducted using tests appropriate for the level of measurement including t-tests, Mann-Whitney U (ordinal data such as number of awakenings), and χ^2 (categorical data such as presence of nausea). Statistical significance for all secondary comparisons will be interpreted at $p < 0.05$. No interim analyses will be conducted.

Human Subjects Protection

Informed Consent

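### Does asking inpatients about saphenous sensation compromise the blinding of the 48 h pain score?

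*Combined protocol and SAP*

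**What the plan says.** All references are to the combined protocol and SAP.

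- **Blinding** (Interventions and Interactions). The OR pharmacy fills the elastomeric pump with ropivacaine or saline according to a sealed envelope. The protocol then states: "The patients, physicians, nurses and investigators will be blinded to treatment group".
- **In hospital** (same section). Of the daily acute pain service visit it says: "They will be questioned about sleep quality, pain score, opioid side effects, and sensory function in the sciatic and saphenous distributions". It adds: "This information will be recorded by the acute pain management team". Separately, "opioid administration and pain scores will be recorded by nursing staff on the patient care record".
- **After discharge.** Under Setting, "all patients will have daily follow-up by phone with the regional anesthesia acute pain management team". Under Interventions and Interactions, "Patients will be generally discharged home with peripheral nerve catheters in place on POD #1", with calls 24 and 48 h later. The calls cover pain at rest and on movement, opioid use, awakenings, nausea and vomiting. Sensation is not among the listed items.
- **Timing.** The primary endpoint is the verbal pain score at rest and with movement 48 h after the block. Under Objectives, the reason for that time is that the primary saphenous "block will have resolved, and any saphenous analgesia will be due to the infused solution". Under Background, the usual single-shot block is expected "to provide 12-24h of saphenous analgesia".

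**The concern.** The primary outcome is a subjective 0-10 rating obtained by interview. Blinding to allocation does not by itself blind anyone to a clinical sign that suggests allocation, and the protocol's own reasoning makes saphenous sensation such a sign: once the primary block has gone, numbness points to ropivacaine and normal feeling points to saline. One team asks about sensation, records the answer and later telephones the patient. With discharge on the day after surgery, the call 24 h later falls near 48 h after the block and so usually supplies the primary score. No sentence separates the two tasks or withholds the sensory answer. If the person asking had guessed the arm, the way the question was put or the answer noted could shift the score. At stake would be the double-blind claim and the false-positive rate of the primary comparison.

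**Working it through.** **1. Who could know what, and when**

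*Patient at home at 48 h (the usual case).* The score comes from a call whose listed items do not include sensation. The only sensory information is an answer given before discharge, generally on the day after surgery. At that point the 12 to 24 h expected of the usual single-shot block has only just ended or is still running, so a saline patient may also be numb. Numbness then says little about the arm; normal feeling says somewhat more. For bias to arise, the caller must be the person who heard that answer (the protocol names a team, not an individual), must remember it, must draw an inference from it, and must sway the patient's own rating by telephone.

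*Patient still in hospital at 48 h (the exception).* Here sensation is informative, and the pain service may ask about it at the same visit as pain. But nurses, who are blinded, also record pain scores, and the protocol lists pain score before sensory function. The data collection form named in the Appendix is not in the public text and may already set the order. It is not established that the person asking about sensation supplies the primary score.

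**2. The plan's own figure**

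Inputs from Sample Size and Analytical Plan: 37 per arm, d = 0.74 SD, about 1.5 points, two-sided α = 0.025 per comparison, power 0.80. The exact noncentral t calculation gives 37 per arm, with power 0.812. The plan's figure reproduces.

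**3. How large a bias would have to be**

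- Implied SD = 1.5 / 0.74 = 2.03 points.
- SE of the difference = 2.027 × √(2/37) = 0.471 points.
- Critical t (0.9875 quantile, 72 df) = 2.289, so the critical difference = 2.289 × 0.471 = 1.08 points.
- If a fraction f of patients is affected and the arm difference in their scores moves by d points, the difference in means shifts by f × d.
- With no true effect, the rejection rate is P(|T| > 2.289), where T is noncentral t with 72 df and noncentrality (f × d) / 0.471.

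Both f and d (here in points) are assumptions; the documents give neither.

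| f | d (points) | Mean shift (points) | False-positive rate per comparison |
|---|---|---|---|
| none | – | 0 | 2.5% |
| 1/20 | 0.5 | 0.025 | 2.5% |
| 1/20 | 1.0 | 0.05 | 2.6% |
| 1/10 | 0.5 | 0.05 | 2.6% |
| 1/10 | 1.0 | 0.10 | 2.8% |

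A simulation that shifts only a random fraction of patients (200,000 replicates) agrees: 2.56% (1/20, 1.0), 2.63% (1/10, 0.5) and 2.86% (1/10, 1.0).

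Working backwards:

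- A rate of 3.0% needs a mean shift of 0.125 points. At a full point each, that is 0.125 × 37 = 4.6 patients per arm.
- A rate of about 5% needs about 0.27 points, or 0.27 × 37 ≈ 10 patients per arm.
- Shifts of 0.3 and 0.5 points would give 5.5% and 11.6%, but at a full point each they need 30% and 50% of patients affected.

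**The case for a change.** The best case for the concern is that the text is silent, and the silence sits on the primary outcome. The blinding statement covers the treatment group, not a sign that suggests it. The same team is named for the sensory record and for the calls. Two sentences would close the gap: score pain before asking about sensation, and have the 48 h score taken from a script by a team member who has not seen that patient's sensory answer. Neither would alter the sample size, α or the analysis, and neither can be added once data are in.

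The silence stands: the protocol does not separate the two tasks. The rest is weaker.

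- An indirect and often ambiguous clue does not contradict a statement that people are blinded to allocation.
- The first safeguard repeats the order in which the protocol already lists the items, which the form may already fix, and shows no gain for an endpoint collected mostly by telephone.
- The second is not obviously cheap. The visits and calls are also clinical follow-up, so withholding an answer means splitting people or records within one clinical team whose staffing the documents do not give.
- Neither reaches the more direct route. The patient produces the rating and can feel whether the leg is numb, whoever asks.

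**Conclusion.** The concern does not hold. No stated number, rule or property of the design is shown to be wrong, and the plan followed as written still gives a sound comparison. The saline control, pharmacy preparation and general blinding are in place, and in the usual case the 48 h score is taken in a call that does not list sensation. For patients still in hospital, blinded nurses also record pain.

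In the assumed scenarios affecting up to 1 patient in 10, the false-positive rate per comparison stays between 2.5% and 2.8%. Larger biases can be computed, but nothing in the documents supports the share of patients they would need.

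This conclusion rests on three readings: that most patients go home on the day after surgery, as the protocol expects; that the 12 to 24 h given for the usual single-shot block applies roughly to the study's primary block; and that the calls keep to their listed items. Who asks which question, and in what order, is operational detail that a team may reasonably settle outside the protocol.

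### The primary 48 h t-test makes no use of the preoperative pain score already collected; a pre-specified ANCOVA would add precision at almost no cost, by an amount the documents do not fix

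*Combined protocol and SAP*

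**What the plan says.** The Analytical Plan defines the primary analysis in one sentence: "The primary analysis will consist of a direct comparison between treatment groups at 48 hours using an independent t-test". It is done twice, for pain at rest and pain with movement, each at alpha = 0.025. No covariate is named.

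The section on Interventions and Interactions records a baseline on the outcome's own 0-10 range, before any sedation: "Study participants will be asked to report a preoperative baseline pain score (Numeric Pain Scale (0-10))". Allocation comes later, once both blocks have been shown to work: "Patients with evidence of sciatic and saphenous nerve block will be randomized to receive a postoperative continuous infusion". The baseline score therefore cannot be influenced by treatment group.

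The only use the Analytical Plan makes of baseline data is that "treatment group characteristics will be compared using descriptive statistics". Its general statement is that, where possible, "all analyses will be conducted using the general linear model (e.g., t-test)". A covariate would fit within that framework, but the only example given is the t-test.

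The Sample Size section sets 74 patients, 37 per group, for power 0.80 at d = 0.74, which it equates to "approximately 1.5 points on a 0 -10 pain scale in our pilot data". It adds: "Differences smaller than this magnitude are unlikely to be clinically meaningful".

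**The concern.** When a pre-randomisation score predicts the outcome, including it in the model estimates the same treatment difference with a smaller standard error. Here the score is already planned, the software and model class are already named, and only a sentence is missing.

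Two things are at stake. The first is power at the plan's own target difference and a somewhat narrower interval around the estimate. The second is what happens if the descriptive table shows the groups to differ in preoperative pain. The plan has no rule for that, and an adjustment chosen after seeing the table would be post hoc.

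The benefit should not be presented as detecting smaller effects, since the plan itself regards those as unlikely to matter clinically.

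**Working it through.** **Inputs from the documents.** n = 37 per group; d = 0.74; two-sided alpha = 0.025 per comparison; 1.5 points taken as equivalent to 0.74 SD.

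**Assumed input.** r, the within-group correlation of preoperative pain with 48 h pain. The documents give no value, so a range is shown.

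**Step 1: the plan's own figure.**
- SD = 1.5/0.74 = 2.03 points.
- Standard error of the difference = 2.03 × √(2/37) = 0.471 points.
- Noncentrality = 0.74/√(2/37) = 0.74/0.2325 = 3.18, with 72 degrees of freedom.
- Noncentral-t power = 0.812. The smallest group size reaching 0.80 is 37, so the stated sample size reproduces for the unadjusted test.

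**Step 2: ANCOVA with baseline pain as the only covariate.**
- Residual degrees of freedom: 71.
- Variance of the adjusted difference, in SD² units: (2/37) × (1 − r²) × (1 + 1/70). The last factor is the average price of estimating the slope when the groups differ by chance at baseline.
- Noncentrality = 0.74/√variance.
- Half-width of the 97.5% interval = t(0.9875, df) × 2.03 × √variance.

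| Analysis | Power at d = 0.74 | Half-width (points) |
|---|---|---|
| t-test | 0.812 | 1.079 |
| ANCOVA, r = 0 | 0.806 | 1.087 |
| ANCOVA, r = 0.1 | 0.810 | 1.081 |
| ANCOVA, r = 0.2 | 0.823 | 1.065 |
| ANCOVA, r = 0.3 | 0.844 | 1.037 |
| ANCOVA, r = 0.4 | 0.874 | 0.996 |
| ANCOVA, r = 0.5 | 0.910 | 0.941 |

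Power equals that of the t-test at r = 0.12. Without the (1 + 1/70) factor the ANCOVA figures would be slightly higher (0.829, 0.850 and 0.914 at r = 0.2, 0.3 and 0.5), so the table is the more cautious version.

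**Step 3: chance imbalance.**
- SD of the baseline mean difference = √(2/37) = 0.232 baseline SD.
- In 5% of trials the groups differ, in either direction, by more than 1.96 × 0.232 = 0.46 baseline SD.
- A difference of that size shifts the unadjusted estimate by r × 0.456 × 2.03, which is 0.18, 0.28 or 0.46 points at r = 0.2, 0.3 or 0.5.

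This is the mechanism of Step 2 seen in a single trial. It is not an additional gain.

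**Step 4: does the result survive bounded scores?** Scores were simulated, rounded and clipped to 0-10, with 40,000 trials per setting. The assumed control mean was 3 to 5; the assumed baseline mean was 2 with SD 3 before clipping.
- Type I error was 0.024 to 0.027 for both methods, against a nominal 0.025.
- At a latent correlation of 0.3, power rose from 0.802 to 0.828 (control mean 5), 0.797 to 0.826 (mean 4) and 0.781 to 0.812 (mean 3).

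**Step 5: if success on either endpoint is enough.** The plan does not state the success rule. With both effects at 0.74 and an assumed rest-movement correlation of 0.5, simulated power is about 0.92 unadjusted and 0.95 with ANCOVA at r = 0.3. At an assumed correlation of 0.8 the figures are about 0.88 and 0.91. In absolute terms the gain is somewhat smaller on that reading.

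**The case against.** The strongest reply is that nothing is broken. The test, time point and alpha split are all specified, the sample size matches the test, and choosing between two valid analyses is the investigators' decision. That stands, and it is why this is only an optional improvement.

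The second reply is that r may be small. The baseline is one score, not separated into rest and movement, and taken before surgery and block. Every patient then has a sciatic infusion and opioids, and is told to respond to breakthrough pain by adjusting the sciatic pump, taking opioids, or both. Treatment that follows pain could compress the 48 h scores and weaken their link to baseline. At r = 0.2 the gain is only 1.1 percentage points of power and 0.014 points of half-width; below r = 0.12 ANCOVA loses slightly. This also stands and limits the expected benefit. It does not remove the asymmetry: at most about 0.6 percentage points lost, against 3.2 gained at r = 0.3 and 9.8 at r = 0.5.

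Third, under randomisation the t-test's standard error already allows for chance imbalance, so the shifts in Step 3 are neither bias nor a second benefit. That is correct.

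Fourth, a replacement text must not be less complete than the present plan. It should leave the nonparametric fallback in place and say what happens to a missing baseline. If ANCOVA dropped one patient per group for that reason, power at r = 0.2 would be 0.811 and the gain would be gone. The Informed Consent section requires the necessary study data before sedation, so few baselines should be missing, but a rule is easily written.

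**Conclusion.** The point holds as a missed low-cost gain in precision, not as an error. The baseline score is collected, it precedes randomisation, and the primary comparison ignores it. Relative to 0.812 for the t-test, power per comparison would lie between 0.806 and 0.910 for r from 0 to 0.5.

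These figures rest on the plan's n, d and alpha, an SD of 2.03 points inferred from its pilot statement, complete data on all 74 patients, and an assumed r. Only at r of about 0.3 or more would the difference be readily visible, and no part of the documents supports a particular value. Priority is low: worth doing because it is cheap, not because the trial's conclusion depends on it.

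**What to change.** In the Analytical Plan, replace the primary-analysis sentence, before unblinding, with text such as:

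> For rest pain and movement pain separately, the primary analysis is an ANCOVA of the 48 h score on treatment group and preoperative pain score (0-10), two-sided at alpha = 0.025 each. A missing preoperative score is replaced by the mean of all observed preoperative scores, regardless of group. The unadjusted t-test is a sensitivity analysis.

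Leave the existing Mann-Whitney provision in place.

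Type of operation (arthrodesis or fracture fixation) should be either left out or written in as a fixed covariate now, not kept as an option. The documents give neither the case mix nor an effect of operation type, so its value cannot be judged. If both covariates were included and neither predicted the outcome, power would be 0.7995, a loss of about 1.3 percentage points.

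The cost is this wording and a few lines of SAS within the general linear model already named. Residual degrees of freedom fall from 72 to 71. No new data, visits or change in sample size are needed, and the type I error allocation is unchanged.
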